2.9 COVID-19

It is noted that particular attention may need to be given to the impact on key efficacy or safety assessments as a result of the COVID-19 pandemic. Consideration of the different areas of impact has been made as described below.

Protocol deviations related to COVID-19 will be recorded under separate categories indicating the type of deviation and that this was due to COVID-19. The assigned categories will be presented in the protocol deviation listing and table summary of major deviations as described in [Section 3.2](#).

Subjects who prematurely discontinue the study due to COVID-19 will record this as their reason for withdrawal and this will be included in the summary of reasons for withdrawal as described in [Section 3.1](#).

Subjects with a modification, interruption or who permanently stop IMP due to COVID-19 will record this as the reason for modification and this will be presented in the summary and listing of IMP modifications as described in [Section 3.5](#).

Missing efficacy data will be subject to the imputation and analysis methods described in [Sections 4.4.4.1](#) and [4.4.4.2](#). Missing data due to COVID-19 will be assumed to be Class 1 missing data (due to reasons other than being non-ambulatory or physically unable to perform the test / assessment) and handled accordingly. The tipping point analysis described in [Section 4.4.4.3](#) will assess the impact of the missing data on the primary analysis.

In order to provide supportive information for interpretation of the key efficacy and safety analyses, a summary of the number and percentage of subjects with missing assessments at each scheduled visit will be presented by treatment group and overall for the following selected data on the ITT analysis set in the target population (efficacy data) or safety analysis set in the overall population (safety data) as appropriate:

- All primary and key secondary efficacy assessments

- Clinical laboratory
- Vital signs
- Electrocardiogram
- Echocardiography
- Pulmonary function test

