4.2.1 Functional Key Secondary Efficacy Variables

4.2.1.1 Time to Rise from Floor

The mean change from baseline in time to rise from the floor after 18 months of treatment with givinostat versus placebo will be assessed. Time to rise from the floor will also be graded by functional evaluators according to standardised scales (see Appendix 7.2).

Summary statistics of time to rise from floor observed values and change from baseline will be presented by visit and treatment group. A plot of the average time to rise from the floor over time by treatment group will be produced.

A shift table showing the movement of subjects with respect to functional adaptation options employed for rising from the floor from baseline to 18 months after treatment will be presented by treatment group.

Note that where subjects have stopped the test prematurely, this is equivalent to not completing the test and therefore the missing time to rise from floor will be imputed according to the rules in Section 4.4.4 for summaries, plots and analyses.

Furthermore, in order to additionally assess the time to rise from floor data in terms of velocity rather than time, a reciprocal transformation will be applied to convert the timed results to appropriate units of velocity, according to the following conversion:

$$\text{Velocity (1/second)} = 1 / \text{Completion time (seconds)}$$

where this conversion is applied following any imputation of missing data as described in Section 4.4.4. The summary statistics and plot described above will be repeated for these transformed values. Analysis of this endpoint (described in Section 4.4.2) will also be repeated on the transformed scale.

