4.4.4 Handling of Missing Data

4.4.4.1 Classification and Imputation

For the efficacy analyses, any missing data for continuous values for a subject will be classified as follows:

1. the subject has missing data due to reasons other than being non-ambulatory or physically unable to perform the test / assessment
2. the subject has missing data due to being either non-ambulatory or otherwise physically unable to perform the test / assessment.

Any missing values classified as 1 will be imputed using the mean of all non-missing values for the respective measurement and timepoint across all subjects randomised to the respective treatment and in the respective concomitant steroid stratum and Group (i.e. Group A, target population or Group B, off-target population).

Any missing values classified as 2 will be imputed by setting the value to zero or to twice the maximum non-missing value recorded across all subjects depending on the directionality of the test.

In all cases, imputation of any data classified as 1 will be completed first, followed by imputation of any data classified as 2.

Classification and imputation of missing data will be completed prior to any transformation of the data for analysis. For example transformation of the timed function test results for presentation of velocity or any log transformation applied as needed (per Section 4.4.2).

For binary or time to event variables where missing data means that the binary response or time to event cannot be determined, the missing data from which the variable is derived (e.g. 6MWT values) will first be classified and imputed, as described above, in order to then derive the binary response or the time to event. Exceptions to this are where the criteria for deriving the binary response themselves refer to presence of missing data, for example loss of ambulation. The classification described above will be used for the relevant missing data in these cases in order to confirm physical inability to complete the respective test. Further details are given below regarding the rules for derivation of the binary endpoints in the presence of missing data.

For the NSAA assessment, where the total score is a sum of ordinal item scores, imputation of Class 1 and Class 2 data will follow a different approach as defined in Appendix 7.5.4.

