The rules for classifying missing data from the responses on the eCRF and any additional considerations for imputation are given in Appendix 7.5 for each respective endpoint. Unless otherwise stated, only the value of interest for analysis will be classified and imputed. For example, the 'duration' for the 4SC assessment will be imputed but not the 4-stair ascent grading.

Note that missing data at any scheduled timepoint should be imputed according to the above rules. This includes any scheduled timepoints after a subject withdraws early. In these cases, where the final assessment prior to withdrawal was missing and determined to be Class 2 missing data, all missing assessments post withdrawal will also be considered Class 2. Otherwise, these will be considered Class 1. Note that where this applies to an NSAA assessment, 'Class 1' will refer to the scenario where

'Was assessment attempted?' = 'No'. Where a date of assessment is required, the predicted date for imputed timepoints post withdrawal will be used. The same approach will be followed for any completely missing visits prior to withdrawal or completing the study, where no information has been entered into the respective CRF assessment page indicating whether or not it was performed.

Where data entered into the CRF for an assessment are ambiguous such that they do not reflect any of the expected responses outlined in Appendix 7.5 and therefore missing data cannot be classified, a worst case approach will be followed and the missing data will be assumed Class 2.

A review will be performed at the BDRM to confirm correct classification of missing data. This may identify data entered into the CRF assessment page which comply with Appendix 7.5 but additional information is available to contradict the classification (for example in comments). Any such cases will be assessed on a case by case basis to determine the appropriate classification to be applied.

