4.4.4.3 Tipping Point Sensitivity Analysis

In addition to the above methods for handling missing data, if the treatment effect on the primary analysis is significant, a 'tipping point' sensitivity analysis of the primary outcome will be performed. This analysis assesses the impact of missingness across a continuum of assumptions until the 'tipping point' is identified. This is the point at which the assumption regarding the effect of the treatment in subjects with missing data nullifies or reverses the treatment effect obtained in the primary analysis. Implementation of this sensitivity analysis mimics standard multiple imputation and is described below:

1. For any Class 1 missing 4SC values, use the mean and SD of all non-missing values for the respective treatment group to generate the imputed values from a normal distribution. Note that any Class 2 missing 4SC values should continue to be imputed with twice the maximum non-missing value recorded across all subjects as applicable per the above rules.
2. Implement Step 1 10 times so that 10 complete datasets are produced. For each of these datasets, find the change from baseline to 18 months in 4SC values for each subject.
3. Analyse the 10 complete datasets; this should be performed as described in Section 4.4.2 using the PROC MIXED approach described in Section 4.4.4.2.
4. Combine the results from the 10 data sets using Rubin's methods via PROC MIANALYZE for inference.
5. Repeat Steps 1 to 4 but now with an appropriate small shift ($+\delta$) applied to the individual subject values for the change from baseline in 4SC in the givinostat treatment group (but not to the placebo group). This shift is applied after step 2, i.e. after the generation of the datasets including any imputation, and after finding the change from baseline values but prior to the analysis of these. The directionality of the shift will be such that this reduces the treatment difference between givinostat and placebo.
6. Display the estimated treatment effect and associated 2-sided CIs vs degree of shift.
7. Repeat Steps 5 and 6, increasing the shift each time as $+2\delta$, $+3\delta$, ..., $+(\text{treatment effect seen in the primary analysis})$.
8. Identify the tipping point where $p > 0.025$.

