7.5 Missing Data Classification and Imputation Rules

7.5.1 Time to Climb 4 Standard Stairs (4SC)

Class 1 – ‘Was assessment performed and completed?’ = ‘No’.

Class 2 – ‘Was assessment performed and completed?’ = ‘Yes’ but ‘Duration’ is missing and ‘4-stair ascent grading’ response is ‘1 = Unable to climb 4 standard stairs’. Note that if the grading is >1 but the ‘Duration’ is genuinely missing, this should be treated as Class 1 missing data.

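### SAP 7.5.1 classes every 4SC entered as not performed and completed as Class 1 without asking why, so a boy unable to climb can receive his group's mean rather than the worst-case value that SAP 4.4.4.1 prescribes

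*SAP*

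**What the plan says.** SAP 4.4.4.1 (Classification and Imputation) defines two classes by cause. Class 2 applies when "the subject has missing data due to being either non-ambulatory or otherwise physically unable to perform the test / assessment"; any other reason is Class 1. Class 1 values are replaced by the mean for the same treatment, steroid stratum and Group at that visit. For 4SC, SAP 4.4.4.2 replaces Class 2 values by twice the largest time recorded in any boy.

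Appendix 7.5.1 turns this into an eCRF rule for the primary endpoint. The first branch is "Class 1 – ‘Was assessment performed and completed?’ = ‘No", with no condition on the reason. Class 2 needs the answer 'Yes', a missing duration, and that the "4-stair ascent grading’ response is ‘1 = Unable to climb 4 standard stairs".

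Three further provisions matter:

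- **Visits after withdrawal (4.4.4.1).** If the final assessment before withdrawal was Class 2, "all missing assessments post withdrawal will also be considered Class 2. Otherwise, these will be considered Class 1".
- **Blinded data review (4.4.4.1).** The review must confirm the classification and may deal, case by case, with entries that "comply with Appendix 7.5 but additional information is available to contradict the classification". Entries that match none of the expected responses default to Class 2.
- **COVID-19 (2.9).** "Missing data due to COVID-19 will be assumed to be Class 1 missing data", so some 4SC 'No' entries belong in Class 1.

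**The concern.** The general rule asks why the value is missing; the 4SC rule does not. For a boy who tries and cannot finish, or who is not tested because he no longer walks, 'No' is a natural answer to a question that joins performed with completed. Under 7.5.1 that answer makes him Class 1. To reach Class 2, the site must record as performed and completed a climb that he could not do.

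The two classes give very different values on the primary endpoint: an average time or twice the worst time in the trial. If the misfiled visit was his last before withdrawal, his later missing 4SC visits are Class 1 too.

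The tipping-point analysis in 4.4.4.3 does not test this. It takes the classes as given and, for Class 1, says to "use the mean and SD of all non-missing values for the respective treatment group to generate the imputed values from a normal distribution".

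**Working it through.** **1. The rules side by side (SAP Appendix 7.5)**

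| Test | 'No' at the first question | Route to Class 2 |
|---|---|---|
| 4SC (7.5.1) | performed and completed = No: Class 1 | Yes, duration missing, grade 1 |
| Rise from floor (7.5.2) | performed = No: Class 1 | performed = Yes, duration missing, grade 1 or 2 |
| 6MWT (7.5.3) | performed = No: Class 1 | performed = Yes, stopped early, duration and distance missing |
| 10-metre (7.5.7) | performed = No: Class 1 | performed = Yes, completed = No, distance and duration missing, grade 1 or 2 |
| NSAA (7.5.4), myometry (7.5.5) | split by reason | not attempted, or an element not attempted, because physically unable |

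Only 4SC merges performing and completing into one answer and sends its 'No' to Class 1. For rise from floor, 6MWT and the 10-metre test the gap is narrower: it concerns a boy who is not tested at all because he is unable. NSAA and myometry follow 4.4.4.1 as written. The worst-case default does not clearly help, because a plain 'No' is one of the expected 4SC responses.

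**2. Size for one boy (illustration)**

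The plan states no figure for this, so there is none to reproduce.

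From the documents: 110 boys at 2:1, so 37 placebo and 73 givinostat; difference 2 s; SD 3.094 s, used here as the within-arm SD (SAP 2.5 calls it that; the protocol synopsis also calls it overall). Assumed: mean 18-month 4SC of 6 s, and a largest recorded time (Max) of 10, 20 or 30 s. No covariates.

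Start: SE = 3.094 × √(1/37 + 1/73) = 0.624; t = 2/0.624 = 3.20 on 108 df; two-sided p = 0.002; critical t = 1.982.

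Moving one boy from Class 1 (6 s) to Class 2 (2 × Max) is a jump J = 2 × Max − 6 = 14, 34 or 54 s. His arm mean moves by J/n, and the pooled sum of squares rises by J²(1 − 1/n).

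| Max (s) | Boy on placebo: difference, SE, t | Boy on givinostat: difference, SE, t, p |
|---|---|---|
| 10 | 2.38, 0.680, 3.50 | 1.81, 0.680, 2.66, 0.009 |
| 20 | 2.92, 0.902, 3.24 | 1.53, 0.905, 1.69, 0.093 |
| 30 | 3.46, 1.208, 2.86 | 1.26, 1.214, 1.04, 0.30 |

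For one givinostat boy, t falls to 1.982 at Max = 16.7 s (15.7 s for an assumed mean of 4 s, 17.7 s for 8 s).

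**3. Where the effect comes from**

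At Max 20 s, the mean shift alone gives t = 1.53/0.624 = 2.46, still significant. The variance added by one 40 s value takes it to 1.69.

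**4. Other scales, one givinostat boy, same standardised effect (2/3.094)**

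- Log scale, jump ln(2 × Max/6)/SD with an assumed log SD of 0.3 to 0.5: t between 2.96 and 2.16, p between 0.004 and 0.033.
- Velocity (4/time), assumed SD 0.2 to 0.4 stairs/s: t about 2.9 to 3.1, p below 0.005 at each Max.

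**The case against.** The strongest reply is that the plan already has a control. The blinded review is mandatory and expressly covers entries that fit Appendix 7.5 but are contradicted elsewhere, which describes a compliant 'No' from a boy known to be unable. That stands in part. The review works case by case, needs contradicting information to exist, and has no written criteria for what counts.

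Second, sites may have been meant to treat inability as a graded result, entering 'Yes' with grade 1 and keeping 'No' for tests not done. The grading scale points that way. The eCRF guide and the file notes listed in the addendum are not shown, so this can be neither confirmed nor excluded. SAP 4.2.1.1 says of a rise from floor stopped early that "this is equivalent to not completing the test and therefore the missing time to rise from floor will be imputed". That shows how the SAP thinks about stopping early, but it concerns another test and does not say which 4SC box a site ticks. A boy never tested because he is non-ambulatory remains a plain case for 'No'.

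Third, the p-values above depend largely on the twice-maximum rule and on assumed values. That is correct and limits what they show.

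A reader might also infer more than the documents support:

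- That a misfiled 4SC drops a boy from the loss-of-ambulation count. It cannot: that endpoint (4.3.8, 7.5.14) uses only the 6MWT and 10-metre entries.
- That all his later visits become Class 1. This follows only if the misfiled assessment was the last before withdrawal.
- That the rule favours givinostat. Nothing shows this: if coding does not depend on arm, no shift is expected under the null, and if the drug works and more placebo boys are unable, misfiling on average dilutes the mean difference.

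**Conclusion.** The inconsistency holds. Appendix 7.5.1 as written can put a physically unable boy in Class 1 on the primary endpoint, against SAP 4.4.4.1, and the blinded review reduces this without closing it. None of the four changes in the SAP addendum touches 7.5.1, 7.5.2, 7.5.3 or 7.5.7.

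The arms are affected differently. Leaving one unable placebo boy in Class 1 lowers the mean difference but changes the test little. Leaving one unable givinostat boy in Class 1 can preserve a significant result that the SAP's own definition would remove, once the largest recorded time is about 17 s or more. That threshold rests on an assumed mean of 6 s, the untransformed scale and no covariate adjustment. On the log scale the result stays significant, and the velocity analysis, which is supportive only, moves little. The documents do not show that any boy was misfiled. This should be corrected, but it is not evidence that a result is wrong.

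**What to change.** In 7.5.1, state that grade 1 with a missing duration is Class 2 whichever answer was given to the performed-and-completed question.

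For every other 'No' on 4SC, rise from floor, 6MWT and the 10-metre test, have the planned blinded review apply a pre-written list of evidence from the same visit and assign Class 2 when it is met:

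- the test's own lowest grades (rise from floor 1 or 2; 10-metre 1 or 2);
- 10-metre grade 1 or 2, for the 6MWT;
- for any of the four, NSAA not attempted because of physical inability;
- a recorded comment or reason, if one exists. The SAP shows a reason field only for NSAA and myometry, so the rule should not depend on one.

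Report the number reclassified by arm and by test.

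The cost is appendix wording, a short list and derivation code, using data already collected. The price is a few more worst-case values and a higher variance. The change belongs before unblinding. The addendum records changes made after database lock, so that point may have passed; in that case, report the counts by arm and present the reclassified analysis as supportive and post hoc.

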7.5.2 Time to Rise from Floor

Class 1 – ‘Was assessment performed?’ = ‘No’.

Class 2 - ‘Was assessment performed?’ = ‘Yes’ but ‘Duration’ is missing and ‘Rising from floor grading’ response is ‘1= Unable to stand from supine, even with use of a chair’ or ‘2= Assisted Gowers’ - requires furniture for assist in arising from supine to full upright posture’. Note that if the grading is >2 but the ‘Duration’ is genuinely missing, this should be treated as Class 1 missing data.

7.5.3 Distance Walked in 6 Minutes (6MWT)

Class 1 - ‘Was assessment performed?’ = ‘No’.

Class 2 - ‘Was assessment performed?’ = ‘Yes’ but ‘Was assessment completed?’ = ‘Stopped prematurely’ and ‘Duration walked’ is left missing and ‘Distance walked at end of test’ is left missing.

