7.5.4 Physical Function as Measured by NSAA

For the purposes of calculating total NSAA score, classification of missing data should be applied as follows:

Class 1 - Either of the following:

- ‘Was assessment attempted?’ = ‘No’ and the reason given is ‘Declined to perform test’ or ‘Other’. In this case, each item score will be imputed using the mode of the non-missing scores for the same item and visit across all subjects randomised to the same treatment and in the same concomitant steroid stratum and Group (i.e. Group A, target population or Group B, off-target population). If there are multiple mode values then the lowest modal value will be used. The total score will be re-derived as the sum of the 17 imputed item scores.
- ‘Was assessment attempted?’ = ‘Yes’ but one or more of the item scores is missing. In this case one of two possible methods will be followed:

- If ≥ 9 out of 17 items have been completed with ≤ 8 missing, then the missing item scores for that subject at that visit will be imputed using the mode of the non-missing item scores for the subject and visit. If there are multiple mode values then the lowest modal value will be used. The total score will be re-derived as the sum of the 17 non-missing and imputed item scores.
- If ≤ 8 out of 17 items have been completed with ≥ 9 missing, then the missing item scores for that subject at that visit will be imputed as zero. The total score will be re-derived as the sum of the 17 non-missing and imputed item scores.

Class 2 - 'Was assessment attempted?' = 'No' and the reason given is 'Unable to physically perform the test'. In this case all item scores and the total score will be imputed to zero.

For the purposes of calculating cumulative number of failed items, NSAA data will first be classified and imputed according to the above rules and the assessment of item failure will then be determined using the values after imputation.

7.5.5 Muscle Strength Evaluated by Knee Extension and Elbow Flexion as Measured by Hand-held Myometry

Class 1 – Either of the following:

- 'Was assessment attempted?' = 'No' and the reason given is 'Declined to perform test' or 'Other'.
- 'Were all 4 elements of the extension/flexion assessment attempted?' = 'No' and the reason given is 'Declined to perform test' or 'Other'. Any missing elements of the test (left/right knee extension or left/right elbow flexion) will be classified as 1.

Class 2 – Either of the following:

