- 'Was assessment attempted?' = 'No' and the reason given is 'Unable to physically perform the test'.
- 'Were all 4 elements of the extension/flexion assessment attempted?' = 'No' and the reason given is 'Unable to physically perform the test'. Any missing elements of the test (left/right knee extension or left/right elbow flexion) will be classified as 2.

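### SAP 7.5.3 gives no missing-data class to a six-minute walk that was completed but has no recorded distance, and the literal default scores it as 0 m

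*SAP*

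**What the plan says.** SAP 4.4.4.1 sorts missing continuous values into two classes. Class 2 is missing because the boy is non-ambulatory or physically unable; Class 1 is missing for any other reason. A Class 1 value takes the mean of the same treatment, steroid stratum and Group at that visit. For Class 2: "Any missing values classified as 2 will be imputed by setting the value to zero or to twice the maximum non-missing value recorded". SAP 4.4.4.2 fixes this at zero for 6MWT, percent predicted 6MWT and hand-held myometry.

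Appendix 7.5 turns the classes into CRF responses:

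- **6MWT (7.5.3).** Class 1 requires that the test was not performed. Class 2 requires that it was performed, was stopped prematurely, and has neither a duration nor an entry for "Distance walked at end of test".
- **Timed tests (7.5.1, 7.5.2, 7.5.7).** Each adds a note for a test that was done. In 7.5.1, if the grade shows that the boy could climb but the duration "is genuinely missing, this should be treated as Class 1 missing data".
- **Strength (7.5.5).** Both classes depend on a negative answer, either to whether the test was attempted or to "Were all 4 elements of the extension/flexion assessment attempted". The recorded reason then decides the class.

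Where CRF entries are ambiguous, match none of the Appendix 7.5 responses and so cannot be classified, 4.4.4.1 says "a worst case approach will be followed and the missing data will be assumed Class 2". The blinded data review meeting (BDRM) is to confirm the classifications. SAP Addendum 1 changes neither 7.5.3 nor 7.5.5.

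**The concern.** A completed walk with a lost distance is a recording gap in a boy who is known to have walked. Scoring it 0 m treats it as total loss of walking ability. The 6MWT is a formal key secondary endpoint in the Hochberg family (SAP 4.4.5), so a wrong value there enters a confirmatory test.

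The zero also feeds percent predicted 6MWT (7.5.9) and the 10% worsening endpoints (7.5.11, 7.5.12). It satisfies the 6MWT criterion for loss of ambulation, because 7.5.14 equates Class 2 with physical inability. If it falls at the last assessment before withdrawal, 4.4.4.1 makes the later missing visits Class 2 as well.

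**Working it through.** The plan gives no figure to reproduce here. The check is a list of response patterns, followed by an illustration of size.

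**1. Patterns with the distance missing and the test performed (SAP 7.5.3)**

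| Completed? | Duration | Class in 7.5.3 | Result read literally |
|---|---|---|---|
| Yes | recorded | none | default Class 2, 0 m |
| Yes | blank | none | default Class 2, 0 m |
| Stopped early | recorded | none | default Class 2, 0 m |
| Stopped early | blank | Class 2 | 0 m |

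Three of the four patterns have no class, and no performed test can reach Class 1.

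**2. Comparison with the SAP's other rules**

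- By the definition in 4.4.4.1, a value lost from a completed test is missing for a reason other than inability, which is Class 1.
- The timed tests send that situation to Class 1. They rely on a functional grade to show ability. The 6MWT has no grade in 7.5.3, but its completion field shows the same thing.
- The NSAA (7.5.4) has its own rule for an assessment that was attempted but has items missing.
- SAP 4.2.1.2 keeps boys who stopped early in the analysis of distance walked, so stopping early is not in itself meant to equal zero.

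**3. Size for one record at month 18 (illustration)**

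From the documents: 110 boys at 2:1, so 110 × 2/3 ≈ 73 on givinostat and 110/3 ≈ 37 on placebo. Assumed, because the documents give no 6MWT level: baseline 400 m, mean change −40 m (so about 360 m at month 18), and SD of change 60 to 100 m.

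- Shift in an arm mean = distance replaced / n.
- Placebo: 360/37 = 9.7 m. Givinostat: 360/73 = 4.9 m.
- For 300 to 450 m: 8.1 to 12.2 m on placebo, 4.1 to 6.2 m on givinostat.
- The givinostat-minus-placebo difference moves +9.7 m if the boy is on placebo and −4.9 m if he is on givinostat.
- If every boy is equally likely to have the gap, the expected shift is (37/110)(360/37) − (73/110)(360/73) = 0.

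Standard error: with one value displaced by 360 m, the pooled variance is about [107·SD² + 360²(1 − 1/n)]/108. At SD 80 and n = 37 this is (684,800 + 126,097)/108 = 7,508, so the SD becomes 86.7 and the SE rises from 80√(1/73 + 1/37) = 16.1 m to about 17.5 m, or 8%. The same formula gives about 15% at SD 60 and 5% at SD 100.

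**4. Strength (SAP 7.5.5)**

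If the test and all four elements are recorded as attempted but an element has no value, neither class applies, and the literal default gives zero. One such zero would move an arm mean by 1/37 = 2.7% (placebo) or 1/73 = 1.4% (givinostat) of average strength, if it replaced the whole endpoint value. If left and right were averaged, it would be half that.

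**The case against.** The best defence is that the default is not clearly triggered. It is written for ambiguous entries that cannot be classified, and a completed walk with a lost distance is not ambiguous: it fits the Class 1 definition. The BDRM must confirm classifications, and the example it is given is not exhaustive, so a completed walk scored 0 m is something it could well find. Protocol 14.1.6 also requires omissions to be explained and missing data to be resolved. This stands in part. It makes Class 1 the sensible outcome, but no rule states it, and the BDRM example concerns entries that do comply with Appendix 7.5.

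A reader might infer more than the documents support:

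- **That the 6MWT result is biased towards givinostat.** A single placebo record would favour givinostat, but the expected shift is zero if the gap is unrelated to arm. What remains is extra noise.
- **That boys who can walk will be counted as having lost ambulation.** SAP 4.3.8 also requires the 10-metre criterion at the same visit, with both criteria met at every later visit. The 10% worsening must likewise persist to study end (4.3.6). These endpoints are exploratory, with nominal p-values.
- **That strength will be scored zero in the final analysis.** Addendum 1 lists a signed muscle-strength file note of 4 May 2022 whose content is not available. Protocol 10.2 takes three readings per side, so all would have to be lost.
- **That a missing weight sets N/kg to zero.** The default concerns CRF entries for an assessment, and a recorded force is not ambiguous. This would be inference.

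A test stopped early with a duration but no distance is harder. Class 1 would give that boy his stratum mean, although stopping early may itself reflect inability.

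**Conclusion.** The gap is real and narrow. SAP 7.5.3 does not classify a 6MWT that was performed and completed but has no distance. Read literally, the default scores it 0 m, against the SAP's own Class 1 definition and its handling of the timed tests. The primary endpoint is not affected, since 7.5.1 carries the note that 7.5.3 lacks.

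One such record at month 18 would move the placebo mean by about 9.7 m or the givinostat mean by about 4.9 m and raise the SE by roughly 5% to 15%. These figures rest on an assumed 360 m and SD of 60 to 100 m. The documents do not say how often the gap occurs, and the number may be zero.

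For a test stopped early with a duration recorded, 0 m also contradicts the record, but the right replacement is a matter of judgement. For strength, the text of 7.5.5 has the same gap; whether it survives in the final plan depends on the unseen file note.

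**What to change.** - Add to 7.5.3: *If the assessment was performed and completed but the distance is genuinely missing, treat as Class 1.*
- State in 7.5.14 that Class 2 assigned only through the 4.4.4.1 default is not evidence of physical inability.
- For a test stopped early with a duration but no distance, settle the replacement value blind and write it down.
- Add a parallel Class 1 note to 7.5.5 for an element recorded as attempted with no value, unless the file note of 4 May 2022 already covers it.
- If the analysis has already been run, count the affected records by arm and report a sensitivity analysis with the completed tests as Class 1.

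The cost is a few sentences and a small programming change. The downside is slightly less conservative handling of a few records.
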